based treatment in the community for patients actively using cocaine. DC educates patients about important concepts in addiction recovery based on the underlying philosophy that physical, emotional, spiritual, and interpersonal needs must all be addressed to support recovery. Accordingly, the DC manual covers the core topics listed in **Table B.3.2.vi**. Masters-level therapists with DC experience from our previous trials^{41, 42} will be trained and supervised by [name] (Co-I).

Contingency Management (CM). We will use the same high-magnitude CM schedule shown previously to be feasible and effective in facilitating initial cocaine abstinence.¹² Subjects will earn vouchers for cocaine-negative urine samples collected at scheduled clinic visits (MWF) each week. Under an escalating reinforcement schedule, voucher values will begin at \$15 and increase by \$10 for each consecutive negative urine. Provision of a cocaine-positive urine or failure to provide a scheduled sample will result in no vouchers earned and will reset the schedule to the initial value (\$15). Bonus vouchers (\$10) will be given for completing all study-related tasks in a given week. Subjects will redeem their earned vouchers for cash loaded to the ClinCard, a reloadable debit card.

Initial response and re-randomization. Following Phase 1 treatment, the primary outcome of response/non-response will be determined. Subjects who submit 6 consecutive (2 weeks) cocaine negative urine samples by week 4 will be classified as responders. Those who fail to meet response criteria will be classified as non-responders.

During second (Phase 2) treatment:

- Responders will continue to receive their assigned initial treatment, as described below.
- Non-responders in each initial treatment arm will be re-randomized to a second treatment consisting of pharmacotherapy augmentation with either modafinil or placebo.

All subjects will attend three clinic visits per week (MWF) during the 8 week second treatment period.

Table B.3.2.vi. 10 Core Topics for ACT and DC

Second (Phase 2) treatments	ACT	DC
Continued ACT or DC. Twice weekly 1-hour ACT and DC sessions will continue during the 8 weeks of second treatment, covering the core topics shown in Table B.3.2.vi.	Preparing to begin	Planning my recovery
	Values	Stages of recovery
	Making contact with the cost of using	People, places, things
	Creative hopelessness	Self-help groups & support systems
	Control v Willingness	Establishing a support system

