Suicide ideation and behavior assessment. The Columbia-Suicide Severity Rating Scale (C-SSRS: <http://www.cssrs.columbia.edu>) will be used to assess suicidal ideation and behavior occurrence. The C-SSRS involves a series of probing questions asked in the patient interview, integrated with information from other sources, to classify suicidal ideation and behavior into 11 preferred categories. The full assessment will be conducted at the initial intake evaluation for screening and eligibility determination. The initial screening questions will be completed at every study visit for every patient by the trained study nurse. The study site has physicians (Co-I: [name]), psychiatrists, and licensed clinical psychologist (Investigators: [name], [name], [name], [name]) on site with extensive experience in managing suicidal ideation and behavior according to established protocols in our outpatient treatment research clinic.

Analysis Plan

Bayesian framework. The Bayesian approach addresses the following study questions: 1) What is the probability that ACT+CM confers benefit relative to DC+CM on abstinence at end of first treatment; what is the best estimate of this effect and what is its precision? 2) Among non-responders at end of first treatment, what are the relative probabilities that pharmacotherapy augmentation confers benefit at end of second treatment for those initially receiving ACT+CM versus DC+CM; what are the best estimates of these effects and what is their precision? 3) Among responders at end of first treatment, what is the probability that continued ACT+CM confers benefit relative to continued DC+CM at end of second treatment; what are the best estimates of these effects and what is their precision? By estimating the probability that such effects exists, we are assessing the probability that the alternative hypothesis is true, a probability that is, by definition, not accessible to Frequentist methods. The FDA has discussed the use of Bayesian statistical methods to make decisions regarding the efficacy of new treatments as an alternative to Frequentist methods in developing clinical applications.⁷⁵⁻⁸⁰ The current proposal will provide the best, unbiased estimates for the benefit conferred across treatment sequences, conditional upon initial response, while also estimating the probability that such effects

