exist. Posterior distributions can then be used as informative priors for continued monitoring in expansions of treatments and treatment strategies exhibiting initial promise.

Analytic strategy. Broadly, the analytic strategy will use generalized linear modeling. Continuous, dichotomous and time-to-event data will utilize linear, logistic, and proportional hazards regression respectively. Longitudinal analyses will employ generalized linear mixed models. All of these SAS (ver 9.3) procedures permit Bayesian analyses. Primary analyses will use intention-to-treat principles, with missing observations imputed as positive. Secondary analyses will implement joint modeling of observed outcomes and the missing data which is robust to ignorable missingness.^{81, 82} Sensitivity analyses will evaluate robustness of analytic conclusions to missing data. Non-ignorable missing data patterns will be addressed through pattern-mixture modeling methods.⁸¹ Prior distributions for comparison of proportions will use $\sim \text{Beta}(a = 1, b = 1)$ priors. Linear, logistic and Cox Proportional Hazards regression coefficient priors will take the form $\sim \text{N}(\text{mean} = 0, \text{var} = 1 \times 10^6)$ in the linear, log (odds) and log scales respectively. Level one error variances will be specified as $\sim \text{Inverse Gamma}(\text{shape} = 0.001, \text{scale} = 0.001)$; level two variances will use $\sim \text{Uniform}(0, 1000)$ distributions. Sensitivity analyses using optimistic and pessimistic, skeptical priors will evaluate prior assumptions.^{83, 84} Inverse probability weight will permit unbiased effect size estimates in the context of re-randomization. Finally, coding procedures will permit identification of each salient effect. Specifically, at the initial randomization ACT+CM and DC+CM will be coded as 1 and -1 respectively. For the re-randomization: 1) non-responders receiving continuation therapy will be coded 1 while all other participants will be coded 0; 2) non-responders receiving augmentation will be coded 1 versus 0 for all other participants.

Hypothesis testing.

Hyp. 1. Initial treatment with ACT+CM will produce higher response (abstinence) rates than initial treatment with DC+CM. Logistic regression will evaluate cocaine-abstinence rates at week 4 as a function of treatment assignment.

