Hyp. 1.a. The benefit of ACT+CM over DC+CM on initial response (abstinence) rates will be greater in the subgroup of individuals with higher pretreatment EA scores. Adding the interaction term (EA-by treatment) to the logistic regression model will evaluate the moderating effect of EA.

Hyp. 1.b. ACT+CM effects on initial treatment response will be mediated by the primary hypothesized treatment mechanisms, EA and reward sensitivity. In the context of the direct effect of treatment on response, mediational modeling will evaluate the *indirect* effect of treatment on response via EA and reward sensitivity variables, using the product moment method with bootstrapped 95% CI and Bayesian posterior distributions.

Hyp. 2. For initial non-responders, continued ACT+CM treatment with pharmacotherapy (modafinil) augmentation will be most effective in promoting abstinence relative to treatment combinations involving DC and/or placebo. Logistic regression will evaluate cocaine abstinence at the end of second treatment in a set of contrasts: (1) modafinil versus placebo within each initial treatment; (2) the sequence of ACT+CM with modafinil augmentation versus DC+CM with modafinil augmentation.

Hyp. 3. For initial responders, continued ACT+CM will be more effective (higher abstinence rates; < 46% relapse rate) than continued DC+CM. Logistic regression will evaluate cocaine abstinence/relapse at end of second treatment as a function of initial treatment (ACT+CM vs DC+CM).

Power. Power estimates for Hypotheses 1, 2 and 3 will use as the primary outcome (i.e., “response”), two consecutive weeks of cocaine abstinence (BE ≤ 150 ng/mL). Initial treatment response (abstinence) rates are expected to be $\sim 40\%$, based on our previous study¹² and pooled data across cocaine clinical trials⁸⁵; however we predict a difference in response rates, favoring ACT+CM over DC+CM by about 20%, constituting a clinically meaningful treatment effect. Among initial non responders, we expect at least a

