small treatment effect favoring augmentation with modafinil, based on our previous trials.^{29, 31, 32, 43} Among initial responders, we previously observed that approximately 54% remain abstinent (46% "relapse") over an extended period of treatment, up to 12 weeks. Using this estimate for the control group (DC+CM), we predict a difference in response rates, favoring continued ACT+CM by about 15%, translating into a relapse rate of about 30%. Importantly, these effect size estimates are derived from data in which missing data is counted as non-abstinence, which mirrors the way we will be treating missing data for our primary analyses.

Finally, given the uncertainty inherent in pre-existing empirical evidence and even greater uncertainty for conditional probabilities of response, prudence dictated that robust trial planning rely upon probability distributions of plausible effects that take into account the uncertainty of our predictions of effect, rather than simple point-estimates. Adoption of distributional specification of effect sizes and their associated uncertainty required implementation of a Bayesian statistical approach.

Data Simulation Model. Using the above outcome estimates, we conducted a Monte Carlo simulation study to determine predicted power for the planned analyses, taking into account uncertainty in parameter estimates. **Figure B.3.2.x** depicts the trial design with probability point-estimates and 95% Credible Limits for each treatment cell, derived from logistic regression models with vague neutral priors, averaged across $K = 500$ simulations. *Simulated results for anticipated cell sizes are shown in italics.* **Table B.3.2.x** displays estimates of power to detect any benefit ($H_A: \theta > 0$) conferred by the treatment hypothesized as being superior. All primary hypotheses demonstrate a > 80% chance of detecting 0.90 probability of benefit for a sample of $N = 160$. Also shown in **Table B.3.2.x** are the point-estimates and 95% Credible Intervals of specified effects averaging over the $K = 500$ simulations.

Summary. Using data-driven effect sizes that take into account uncertainty, simulation results indicate that with a sample size $N=160$, we have roughly 80% power for all primary hypotheses. Further, we stipulate *a priori* that a > 80% chance of treatment conferring benefit (i.e. $Pr(\Pr \theta > 0 | \text{data}) > 0.80$)

[figure not shown]

Table B.3.2.x.

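### Table B.3.2.x: the second-stage intervals are narrower than the planned within-arm contrasts can give at N=160, and the Aim 2 power of 0.81 holds only if placebo abstinence is very low

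*Combined protocol and SAP*

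**What the plan says.** Question 2 under Bayesian framework asks for the "relative probabilities that pharmacotherapy augmentation confers benefit at end of second treatment for those initially receiving ACT+CM versus DC+CM". Hyp. 2 turns this into logistic-regression contrasts among initial non-responders, the first being "1) modafinil versus placebo within each initial treatment".

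Analytic strategy says that "coding procedures will permit identification of each salient effect". It lists three codes: initial treatment (+1/-1), non-responder continuation (0/1) and augmentation, where "non-responders receiving augmentation will be coded 1 versus 0 for all other participants". It lists no product of initial treatment and augmentation and does not say whether the arms are fitted together. Hyp. 1.a does name its product term: "Adding the interaction term (EA-by treatment) to the logistic regression model will evaluate the moderating effect of EA".

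Data Simulation Model says the simulation was run "to determine predicted power for the planned analyses, taking into account uncertainty in parameter estimates". Its cell rates and cell sizes are in Figure B.3.2.x, which is not shown. Table B.3.2.x then gives:

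| Row | Threshold | Power | Difference | 95% interval | Width |
|---|---|---|---|---|---|
| Aim 1, 1 vs 2 | 0.90 | 0.83 | 0.20 | 0.05-0.34 | 0.29 |
| Aim 2, 5 vs 6 | 0.80 | 0.81 | 0.17 | 0.06-0.27 | 0.21 |
| Aim 2, 7 vs 8 | 0.80 | 0.81 | 0.13 | 0.05-0.21 | 0.16 |
| Aim 3, 3 vs 4 | 0.85 | 0.80 | 0.16 | 0.07-0.25 | 0.18 |

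**The concern.** The Aim 1 comparison uses all 160 participants and has an interval 0.29 wide. The Aim 2 contrasts each use only the non-responders of one arm, split in two, yet their printed intervals are narrower. Halving and then thinning the sample should widen an interval.

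A reader who takes the table at face value expects the trial to estimate each within-arm modafinil effect to about plus or minus 0.1 and to detect it four times in five. If neither is true of the contrasts in Hyp. 2, the stated precision and power for the secondary aims mislead those who will judge the results. A related gap is that the text does not name the model that would yield arm-specific effects.

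**Working it through.** **Inputs.** N=160, taken as 80 per initial arm. Initial response is expected at about 40%, with a difference "favoring ACT+CM over DC+CM by about 20" percentage points. The text does not say which arm the 40% describes, so I take ACT/DC response as 60/40, 50/30 or 40/20. Non-responders are "re-randomized to a second treatment consisting of pharmacotherapy augmentation with either modafinil or placebo"; the ratio is not stated and 1:1 is assumed. I take 5 vs 6 as the ACT pair and 7 vs 8 as the DC pair, which the text does not confirm.

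Cell sizes are 80 x (1 - response)/2:
- ACT: 80 x 0.40/2 = 16, 80 x 0.50/2 = 20, 80 x 0.60/2 = 24.
- DC: 80 x 0.60/2 = 24, 80 x 0.70/2 = 28, 80 x 0.80/2 = 32.

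**Step 1: reproduce Aim 1.** I enumerated all binomial outcomes, formed the posterior of the difference under Beta(1,1), and averaged the limits. With 80 per arm and 60% vs 40%, the mean interval is 0.05-0.34, as printed. Fixed-effect power at Pr > 0.90 is 0.887 against 0.83 stated. Letting the effect vary with SD 0.06 gives 0.833.

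**Step 2: apply the same method to Aim 2.**

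| Contrast, n per cell | Mean width at placebo 0% / 10% / 40% | Power at 5% / 10% / 40% |
|---|---|---|
| 5 vs 6, n=16 | 0.42 / 0.50 / 0.61 | 0.735 / 0.680 / 0.536 |
| 5 vs 6, n=20 | 0.37 / 0.46 / 0.56 | 0.766 / 0.680 / 0.617 |
| 5 vs 6, n=24 | 0.33 / 0.42 / 0.52 | 0.813 / 0.740 / 0.680 |
| 7 vs 8, n=24 | 0.31 / 0.41 / 0.52 | 0.707 / 0.621 / 0.574 |
| 7 vs 8, n=28 | 0.28 / 0.38 / 0.48 | 0.747 / 0.671 / 0.519 |
| 7 vs 8, n=32 | 0.26 / 0.35 / 0.46 | 0.784 / 0.716 / 0.568 |

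The printed widths are 0.21 and 0.16. The vague N(0,10^6) logistic prior narrows intervals when the placebo cell is nearly empty, but not enough. Even if all 160 were non-responders (40 per cell) and placebo abstinence were 0%, the widths would be 0.22 and 0.20 (0.25 and 0.23 under Beta(1,1)). This bound does not depend on which pair belongs to which arm.

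Hand check, n=20 and placebo 10%: SE = sqrt(0.10 x 0.90/20 + 0.27 x 0.73/20) = 0.120. Width = 3.92 x 0.120 = 0.47. Power = Phi(0.17/0.120 - 0.842) = Phi(0.58) = 0.72.

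Over both priors and all three response readings, power at 10-40% placebo abstinence is 0.52-0.77. It reaches 0.81 only at about 5% or less, or up to about 7% with the largest cells by a normal approximation.

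**Step 3: compare the printed intervals with the printed power.** For 5 vs 6, SE = 0.21/3.92 = 0.0536, 0.17/0.0536 = 3.17, and power at Pr > 0.80 is Phi(3.17 - 0.842) = 0.99. For 7 vs 8, SE = 0.16/3.92 = 0.0408, 0.13/0.0408 = 3.19, and power is again 0.99. The table says 0.81.

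Effect uncertainty could bring 0.99 down to 0.81. Since Phi(0.878) = 0.81, the total SD would have to be (0.17 - 0.842 x 0.0536)/0.878 = 0.142, so the effect SD would be sqrt(0.142^2 - 0.0536^2) = 0.13. The same sum for 7 vs 8 gives 0.10. Aim 1 needed 0.06. Effect uncertainty would not explain the narrow intervals in any case.

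**Step 4: Aim 3.** At 70% vs 54%, with 48/32 or 40/24 responders, the mean width is 0.41 or 0.46 against 0.18 printed. Power at Pr > 0.85 is 0.66 or 0.61 (about 0.58-0.68 allowing for method) against 0.80. This row involves no modafinil.

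**Step 5: the codes.** With main effects only, the linear predictor is b0 + b1 x initial + b2 x continuation + b3 x augmentation. If continuation means placebo and augmentation means modafinil, the modafinil-minus-placebo difference is b3 - b2 in both arms. Four coefficients then serve six cells.

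**The case against.** **The placebo rate may be low.** The outcome is two consecutive abstinent weeks in people who have already failed to achieve that, and missing samples count as positive. The rates are in a figure I cannot see, and at about 3-5% the stated power can be reached. This stands, so a reader who infers that Aim 2 is proven underpowered goes beyond the documents. It does not rescue the intervals, which are too narrow even at 0%.

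**The power method has not been recovered.** The fixed-effect calculation overshoots Aim 1 (0.887 against 0.83) and matches only once an effect SD is chosen. This also stands, but it works in the plan's favour: letting the effect vary (SD 0.05-0.10) lowers the 10-40% Aim 2 figures by 0 to 6 points.

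**The codes are not a model.** Analytic strategy lists variables and nowhere says main effects only. Hyp. 2 commits to within-arm contrasts, which separate fits or a product term would deliver. A reader might infer that a pooled analysis will be run; the text does not support that. Nor does it support reading both codes as uninformative about modafinil because the re-randomisation text calls both options augmentation. The Power section and Hyp. 2 tie the word to modafinil, so a definition is enough.

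**A pooled model may have produced 0.81.** An additive fit gives about 0.78-0.88 in scenarios that match the table's differences. That is suggestive, but the text does not identify the model, and the Aim 3 row is off where no pooling over modafinil is possible.

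**The Go rule.** One might conclude that within-arm contrasts would often miss Go. The Summary states its 0.80 rule for the project and does not make each secondary contrast decide it.

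**Conclusion.** The Aim 2 rows of Table B.3.2.x do not describe the within-arm contrasts that Hyp. 2 plans. The interval error rests only on N=160, roughly equal allocation and the table's own differences: printed widths are 0.21 and 0.16, against at least about 0.33 and 0.26 under Beta(1,1) with realistic cells. The intervals are also hard to square with the printed power, which would be about 0.99 at a fixed effect.

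The power shortfall (0.52-0.77 against 0.81) is conditional on placebo abstinence of 10-40%, which is my assumption. The Aim 3 row has the same fault, so the problem lies in the second-stage rows generally and not only in the modafinil coding. The missing model statement is an under-specification. Aims 2 and 3 are secondary, and Hypothesis 1 is untouched.

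**What to change.** 1. Rerun the simulation for the contrasts as Hyp. 2 and Hyp. 3 state them. Restate power and intervals for all second-stage rows of Table B.3.2.x (Aims 2 and 3), even if less favourable. Give the model, cell rates, cell sizes and re-randomisation ratio in the text beside the table.
2. If a pooled modafinil effect was what was powered, say so in Hyp. 2 and label the arm-specific contrasts descriptive.
3. In Analytic strategy or Hyp. 2, state that the Aim 2 model includes an initial-treatment-by-modafinil term or is fitted separately by initial arm. Define the augmentation code as modafinil versus placebo.

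The cost is SAP wording, analysis code and one simulation rerun, with no change to conduct. The stated figures for the secondary aims will look weaker, and arm-specific estimates give up some precision if the modafinil effect is in fact the same in both arms.

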Patients who respond to initial ACT+CM treatment may benefit from continued ACT to prevent relapse. Achieving early cocaine abstinence is a robust predictor of longer term cocaine abstinence.³³ In our previous feasibility study, patients who achieved two consecutive weeks of abstinence under high-magnitude CM used less cocaine during subsequent treatment, regardless of medication received, compared with subjects who failed to achieve initial abstinence.¹² However 15 of the 33 initial responders (46%) “relapsed” during second treatment, as indicated by the first cocaine-positive urine after achieving initial abstinence. Using 46% as a benchmark for measuring improvement, the goal of the proposed study is to construct an optimal adaptive treatment intervention that reduces relapse (<46%) within this subgroup of initial responders with an otherwise good prognosis.

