1. To determine if ACT enhances response to a high-magnitude CM procedure targeting cocaine-negative urines. It is hypothesized that initial treatment (4 weeks) with ACT and CM (ACT+CM) will produce higher response (abstinence) rates than initial treatment that combines standard Drug Counseling with CM (DC+CM).
 - 1.a. To determine if pretreatment EA level moderates the effects of ACT+CM on initial response. It is hypothesized that the benefit of ACT+CM over DC+CM on initial response (abstinence) rates will be greater in the subgroup of individuals with higher pretreatment EA scores.
 - 1.b. To determine if the effects of ACT+CM are mediated by changes in EA and reward sensitivity. It is hypothesized that ACT+CM effects on initial treatment response will be mediated by the primary hypothesized treatment mechanisms, EA and reward sensitivity.

Secondary Aims/Hypotheses:

2. To determine the best sequencing of treatment for initial non-responders. For initial non-responders, it is hypothesized that continued ACT+CM treatment with pharmacotherapy (modafinil) augmentation will be most effective in promoting abstinence relative to treatment combinations involving DC and/or placebo.
3. To determine the best sequencing of treatment for initial responders. For initial responders, it is hypothesized that continued ACT+CM will be more effective (higher abstinence rates; < 46% relapse rate) than continued DC+CM.

Study Design

Overall Research Strategy. We propose an adaptive, two-stage SMART design to test the primary research hypothesis that ACT, when used in combination with CM, will increase initial treatment response rates. Secondary hypotheses will determine the probability of benefit associated with two sequences of treatments, specifically, continued ACT+CM for initial treatment responders (dashed lines in **Figure B.3.2.i**) and continued ACT+CM with modafinil augmentation for initial treatment non-responders (double lines in **Figure B.3.2.i**).

Overview of Study Design. Note: SR=stratified randomization; R=randomization; ACT=Acceptance and Commitment Therapy; DC=Drug Counseling; CM=Contingency Management; PLA=placebo; MOD=modafinil. Abstinent=6 consecutive (2 wks) cocaine-negative (BE<150 ng/ml) urines samples.

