Phase 1 treatments. Consenting subjects will be assigned to one of the two 4-week Phase 1 treatments, ACT+CM or DC+CM, using urn randomization to ensure balance between groups on baseline EA level, coded as "high" if AIS score > 45, or "low"≤ 45. Subjects in both treatments will be scheduled to attend three clinic visits per week (MWF) during the 4-week period. **Two** of these weekly visits will include 1-hour therapy sessions (ACT or DC).

Acceptance and Commitment Therapy-Cocaine Use (ACT). The overarching goal of ACT is to decrease experiential avoidance while increasing acceptance and willingness to experience unpleasant thoughts, feelings, and physical symptoms. More specifically, ACT will assist cocaine patients to notice their internal cravings and triggers, abandon their attempts to manage these triggers via active avoidance, suppression or other control-based strategies, and to make commitments to engage in behaviors consistent with their chosen values or goals. ACT encourages clients to experience thoughts and feelings from an observer perspective, and helps them not to believe distressing thoughts and feelings as if they are literally true and in need of action. ACT treatment will be based on the therapy manual developed and tested previously.^{38, 39} The manual covers 10 core topics listed in **Table B.3.2.vi.** Our experienced ACT therapists will be taught to use the manual as a map with flexibility to "go with the client" so long as issues of acceptance, diffusion, values, and committed action are thoroughly covered. Mindfulness exercises, metaphors, and homework sheets will be used to pursue therapeutic goals, more so than didactic instruction. Masters-level therapists with ACT experience from our previous trial ³⁸ will be trained and supervised by [name] (Co-I) and [name] (Consultant).

Drug Counseling (DC). We will use the manual-guided individual DC modeled after the NIDA Collaborative Cocaine Treatment Study ⁴⁰ and used as the active control therapy in our previous studies.^{38, 41, 42} DC approximates clinical practice as it is considered the most common type of evidence-

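### Hyp. 3 and Hyp. 2 contrast (2) compare ACT with DC inside week-4 response groups, so they are not randomised comparisons and the plan's claim of unbiased estimates is unsupported for them

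*Combined protocol and SAP*

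**What the plan says.** **Allocation.** Under Phase 1 treatments, patients are assigned to ACT+CM or DC+CM "using urn randomization to ensure balance between groups on baseline EA level". Under Initial response and re-randomization, "Responders will continue to receive their assigned initial treatment, as described below", while non-responders in each arm are re-randomised to modafinil or placebo. Nobody is randomised between ACT and DC a second time.

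**Contrasts.** Under Hypothesis testing, Hyp. 3 applies to initial responders: "Logistic regression will evaluate cocaine abstinence/relapse at end of second treatment as a function of initial treatment (ACT+CM vs DC+CM". Hyp. 2 applies to initial non-responders. Its contrast (1) is modafinil versus placebo within each initial treatment. Its contrast (2) is ACT+CM with modafinil versus DC+CM with modafinil.

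**Claims.** Overall Research Strategy says "Secondary hypotheses will determine the probability of benefit associated with two sequences of treatments". Question 3 of the Bayesian framework asks, among responders, "what is the probability that continued ACT+CM confers benefit relative to continued DC+CM at end of second treatment". The same section promises "best, unbiased estimates for the benefit conferred across treatment sequences, conditional upon initial response". Analytic strategy adds inverse probability weights, justified by the re-randomisation. No covariate adjustment or selection assumption is stated for Hyp. 3 or contrast (2).

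**Go rule.** The Summary after the power section takes a posterior probability of benefit above 0.80 as enough to advance to Phase III. It does not say which contrasts may trigger this.

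**The concern.** Week-4 response is an outcome of the first treatment. The Power section predicts that ACT will raise it by about 20 points, and Hyp. 1.a expects the gain to be larger in patients with high EA. If so, the ACT responders include people who would not have responded under DC, and the two responder groups need not have the same prognosis. The same holds for the non-responders left in each arm. The plan regards response as prognostic: in the earlier feasibility study, responders "used less cocaine during subsequent treatment, regardless of medication received, compared with subjects who failed to achieve initial abstinence".

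A posterior probability from either contrast therefore mixes any second-stage effect of ACT with any difference in who reached the group. By itself it cannot show that continued ACT prevents relapse, or that ACT is the better base for modafinil. Someone who relies on the word 'unbiased' would read it as showing exactly that, and could use it to justify Phase III.

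**Working it through.** **1. The plan's own figure.** Table B.3.2.x gives Aim 3 (contrast 3 vs 4) a power of 0.80 at posterior probability 0.85, with average effect 0.16. With 80 per arm (1:1 assumed), responder groups of 32 and 48 (response 40% vs 60%) or 24 and 40 (30% vs 50%), and abstinence of 54% vs 69-70%, I get 0.57 to 0.67. The row does not reproduce from the text; the figure with the cell sizes is not shown. That is a separate matter and nothing below depends on it.

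**2. What the weights do.** With 1:1 allocation at both steps (assumed), a responder has weight 1/(1/2) = 2 and a non-responder 1/(1/2 × 1/2) = 4. Within a response group the weight is constant, so it cancels. In a simulation with no ACT effect on the Phase 2 outcome and a correlation of 0.6 between response and that outcome, the ACT minus DC difference was -0.088 in responders and -0.055 in non-responders on modafinil, each identical weighted and unweighted.

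**3. Hyp. 3, illustration.** Assume response of 60% (ACT) vs 40% (DC), nobody who responds only under DC, and no Phase 2 effect of ACT. DC responders (40% of patients) have abstinence 0.54, the Power section's figure. ACT responders are those same 40% plus 20% who respond only under ACT, with unknown abstinence q. Then

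shift = (0.40 × 0.54 + 0.20 × q)/0.60 - 0.54 = (q - 0.54)/3.

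The chance of passing 0.80 comes from 200,000 simulated trials with Beta(1,1) priors and a normal approximation to the posterior difference:

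| q (assumed) | Shift, points | Pass, no true effect | Pass, true 70% vs 54% |
|---|---|---|---|
| 0.54 | 0 | 0.20 | 0.73 |
| 0.40 | -4.7 | 0.11 | 0.57 |
| 0.20 | -11.3 | 0.03 | 0.34 |
| 0.70 | +5.3 | 0.36 | 0.87 |

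The posterior SD of the difference is about 0.11. With 50% vs 30% response the divisor changes (0.20/0.50 = 0.40): the shifts are 0, -5.6, -13.6 and +6.4 points. The pass rate at true 70% vs 54% is then about 0.67 with no shift, 0.50 at -5.6 and 0.26 at -13.6; with no effect and +6.4 it is 0.37.

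**4. Hyp. 2 contrast (2), same assumptions (60% vs 40%).** ACT non-responders are the 40% who respond to neither therapy (abstinence m). DC non-responders are those plus the 20% ACT-only responders (abstinence r on DC+modafinil). Then

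shift = m - (0.40 × m + 0.20 × r)/0.60 = (m - r)/3.

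This is 0 if m = r, -3.3 or -6.7 points if r is 10 or 20 points above m, and +3.3 if r is 10 points below.

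**5. Selection through EA alone.** Assume half the patients are high-EA, DC response is 55% (low EA) and 25% (high EA), ACT response is 60% in both, and later abstinence is 15-20 points lower with high EA. High-EA share of responders: DC 0.25/(0.55 + 0.25) = 31.25%, ACT 50%. Shift: -(0.50 - 0.3125) × 15 to 20 = -2.8 to -3.8 points. Among non-responders: DC 0.75/(0.45 + 0.75) = 62.5%, ACT 50%, giving +1.9 to +2.5 points.

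**6. A different model.** With a bivariate-normal link between response and Phase 2 outcome, a common correlation of 0.2 to 0.8, 60% vs 40% response and no Phase 2 effect, the responder contrast shifts by -3 to -13 points and the non-responder contrast by -3 to -6. If the correlation is 0.2 under DC and 0.6 under ACT, the responder shift becomes +9 points and false passing rises from 0.20 to 0.47. The sign thus depends on quantities the documents do not give.

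**The case against.** **The conditioning is disclosed.** The framework questions say among responders and among non-responders, and Overall Research Strategy goes on to define its two sequences by response status. That is correct, and it narrows the fault to what is claimed for the contrasts. But disclosing the subgroup does not disclose that randomisation no longer protects a comparison within it, and 'unbiased' asserts the opposite.

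**Bias is not shown.** This stands. The feasibility result compares responders with non-responders. It does not compare patients who respond only under ACT with those who would respond under either therapy, which is what q requires. It also fits early abstinence itself helping later abstinence, in which case there need be no selection. A reader might infer that Hyp. 3 is biased, or biased against ACT. The documents support neither: q, r and m are all assumed, and the routes above disagree in sign.

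**No whole-sample analysis was promised.** A reader might take the weights and the coding for all participants as a whole-sample sequence model left unspecified. Analytic strategy names no such model; the codes are there to identify effects, and Hypothesis testing then lists the contrasts. Its absence is not a defect in the plan.

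**These are secondary aims leading only to confirmatory work.** Aims and Hypotheses does list them as secondary, which limits the severity. The Go rule, however, does not exclude them.

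**Conclusion.** The point holds as a matter of design and wording. Hyp. 3 and Hyp. 2 contrast (2) are not randomised comparisons of ACT with DC, and the claim of unbiased estimates is unsupported for them. It rests only on the allocation text and the plan's own prediction that ACT changes response; it needs no assumed rate.

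The size is unknown and may be zero. In the first model, shifts for Hyp. 3 run from -14 to +6 points across the two response scenarios, and only -3 to -4 through EA alone. All depend on assumed rates; the pass rates likewise describe the assumptions and do not predict this trial's error rates. Hyp. 1 and modafinil versus placebo within each initial arm keep their randomisation. This should be fixed before the secondary results are interpreted; it does not touch the primary comparison.

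**What to change.** **Needed.** In the Bayesian framework, withdraw 'unbiased' for these two contrasts. In Hypothesis testing, say that Hyp. 3 and Hyp. 2 contrast (2) compare groups defined by a post-randomisation response, are not randomised comparisons, and are reported adjusted for baseline EA, which is already collected for the urn randomisation. Say also that adjustment removes only selection running through EA. In the Summary, state that neither contrast alone supports Go.

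**Optional supplement.** Compare ACT-start with DC-start sequences in all 160 patients: responders continue with attendance-based CM, and non-responders continue with abstinence-based CM plus modafinil (and, separately, plus placebo), as the design already specifies. Use one end-of-second-treatment outcome for everyone, for example the two consecutive abstinent weeks in the Power section. The 54% is not on that scale: it comes from relapse "as indicated by the first cocaine-positive urine after achieving initial abstinence". Take the posterior of p × s + (1 - p) × m in each arm, where p is response, s is responder abstinence and m is here abstinence in the relevant non-responder cell.

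State that this contrast includes the Phase 1 effect and the response-dependent CM target, does not isolate second-stage ACT versus DC, and does not replace Aim 3. Also say whether it can support Go. With no Phase 2 ACT effect, and under the step 3 assumptions, the modafinil sequences would still differ by 0.20 × (q - r). With q and r now assumed on the common outcome, that is 0.20 × (0.20 - 0.23) = -0.6 points at one end and 0.20 × (0.70 - 0.18) = +10.4 at the other.

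**Cost.** A few sentences of SAP text, one covariate already collected and, if the supplement is taken up, one outcome definition and a short posterior calculation. No new data are needed. The real price is that two secondary contrasts carry a weaker conclusion.
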